Title: The Benchmark Clinic: An Interdisciplinary Comprehensive Care Model for People with Parkinson

Disease PI: [name].

Version Date: 01/29/2021

Pro00105281

NCT04555720

Research Summary

State your primary study objectives

The purpose of this study is to determine if a "one stop" interdisciplinary benchmark clinic model impacts patient engagement with self-care (primary outcome), treatment compliance, caregiver burden, and/or clinical outcomes (falls, ER visits/hospitalizations, Parkinson's disease motor disability) compared to standard subspecialty care.

State your secondary study objectives

To develop a single-day comprehensive care clinic for people with Parkinson's disease, to address care fragmentation, increase patient engagement, and improve outcomes.

Travel burden and schedule limitations prevent patients from reaching all necessary skilled therapists with training in PD and may negatively impact long term outcomes and engagement with treatment plans.

Please select your research summary form:

Standard Research Summary Template

This is the regular (generic) research summary template which is required for all regular applications (unless your protocol fits under the other research summary templates in this category). Use of these instructions is helpful for ensuring that the research summary contains all necessary elements.

Standard Research Summary

Purpose of the Study

- Objectives & hypotheses to be tested

Does a “one stop” interdisciplinary benchmark clinic model impact patient engagement with self-care (primary outcome), treatment compliance, caregiver burden, and/or clinical outcomes (falls, ER visits /hospitalizations, Parkinson’s disease motor disability) compared to standard subspecialty care?

Background & Significance

- Should support the scientific aims of the research

Parkinson’s disease (PD) management is complex, and medication management alone is not sufficient. Non-motor complaints are often more disabling than motor symptoms. Neurologists are time-limited in their ability to address all aspects of this disease. An interdisciplinary clinic provides comprehensive exposure to allied health professionals and immediate interventions, which are already established as helpful individually (e.g. physical therapy for falls prevention, speech therapy for aspiration prevention). Travel burden and schedule limitations prevent patients from reaching all necessary skilled therapists with training in PD and may negatively impact long term outcomes and engagement with treatment plans.

Published studies of interdisciplinary clinics to date have an expert center and community referral model: 1. see neurologist 2. Get referrals to needed allied health specialties for a later date. This so-called “hub-and-spoke” care model in the Netherlands improved outcomes and lowered cost [1] but developing a similar network is challenging in the United States, where geographic distance and competing hospital networks may fragment care.

We developed a single-day comprehensive care clinic for people with Parkinson’s disease, to address care fragmentation, increase patient engagement, and improve outcomes. Patients are evaluated by social work, physical therapy, occupational therapy, speech therapy, pharmacy, and a physician’s assistant in a scheduled rotation. After these evaluations, the team meets with the physician movement disorders specialist for a team discussion of care needs. Following this meeting, the physician meets with the patient to summarize the results and discuss ongoing care needs. The benchmark day lasts from around 8AM-1:30 PM with a built in 45 minutes for lunch from 12:15-1PM.

REFERENCE: [1] Bloem et al. Health Affairs 2017.

Design & Procedures

- Describe the study, providing detail regarding the study intervention (drug, device, physical procedures, manipulation of the subject or the subject’s environment, etc.). Discuss justifications for placebo control, discontinuation or delay of standard therapies, and washout periods if applicable. Identify procedures, tests and interventions performed exclusively for research purposes or more frequently than standard of care. Include alternative therapies, concurrent therapies discontinued per protocol, risk benefit ratio, and use of tissue/specimens. Discuss monitoring during washout periods if applicable. Include brief description of follow-up, if any.
- **Visit 1:** 0-3 months before benchmark clinic surveys on day of consent: approximately 30 minutes. Physical exam with Parkinson’s disease motor disability score as part of normal clinic visit that day. Participants will be randomized on a 1:1 basis to experimental vs control groups after consenting and prior to the start of this study visit. Subjects will complete the pre-clinic quality of life, treatment adherence, and self-efficacy surveys at this visit.
- **Visit 2:** Benchmark clinic from 8AM-1:30PM: Patients see social work, physical therapy, occupational therapy, speech therapy, and pharmacy in a scheduled rotation for about 45 minutes each. Social work and pharmacy visits may be done earlier in the week depending on provider and patient availability. After these evaluations, the team meets with the physician movement disorders specialist for a team discussion of care needs. Following this meeting, the physician meets with the patient to summarize the results and discuss ongoing needs and action items and enter appropriate referrals and orders. The benchmark day lasts from around 8AM-1:30 PM with a built in 45 minutes for lunch from 12:15-1PM.

- **Visit 3:** 3-6 months Follow up study point surveys: approximately 30 minutes. The control group will not participate in the benchmark clinic (Visit 2) and instead, their physician movement disorders specialist will make allied health referrals as part standard clinical care during a physician visit on the same day as study visit 2. They will still complete visit 3.

The control group will not participate in the benchmark clinic (Visit 2) and instead, their physician movement disorders specialist will make allied health referrals as part standard clinical care during a physician visit on the same day as study visit 1. They will still complete visit 3.

Selection of Subjects

- List inclusion/exclusion criteria and how subjects will be identified.

Subjects will be from the patient population with Parkinson's Disease over the age of 30. Caregivers will be required for participation. All subjects must be able to provide consent. Subjects will be contacted first with the phone script by a study email address.

Subject Recruitment and Compensation

- Describe recruitment procedures, including who will introduce the study to potential subjects. Describe how you will ensure that subject selection is equitable and all relevant demographic groups have access to study participation (per 45 CFR 46.111(a) (3)). Include information about approximately how many DUHS subjects will be recruited. If subjects are to be compensated, provide specific prorated amounts to be provided for expenses such as travel and/or lost wages, and/or for inducement to participate.

This study will be discussed with Parkinson's Disease patients when considering referring them to our already established benchmark clinic. All patients already scheduled for an upcoming benchmark clinic will be called or emailed to see if they would like to enroll.

Patients who are randomized to standard care will have the opportunity to participate in the benchmark clinic within 1 year but not as part of this study. 200 subjects will be enrolled (100 benchmark clinic and 100 controls for standard of care). Payment of the subject will be upon completion of visit 2 (the benchmark visit or standard visit)

Subject's Capacity to Give Legally Effective Consent

- If subjects who do not have the capacity to give legally effective consent are included, describe how diminished capacity will be assessed. Will a periodic reassessment occur? If so, when? Will the subject be consented if the decisional capacity improves?

Subjects with diminished capacity will not be consented.

Study Interventions

- If not already presented in #4 above, describe study-related treatment or use of an investigational drug or biologic (with dosages), or device, or use of another form of intervention (i.e., either physical procedures or manipulation of the subject or the subject's environment) for research purposes.

There are no study interventions.

Risk/Benefit Assessment

- Include a thorough description of how risks and discomforts will be minimized (per 45 CFR 46.111(a) (1 and 2)). Consider physical, psychological, legal, economic and social risks as applicable. If vulnerable populations are to be included (such as children, pregnant women, prisoners or cognitively impaired adults), what special precautions will be used to minimize risks to these subjects? Also identify what available alternatives the person has if he/she chooses not to participate in the study. Describe the possible benefits to the subject. What is the importance of the knowledge expected to result from the research?

There are no physical risks associated with this study. Comprehensive interdisciplinary care may help with the subjects engagement with Parkinson's treatment, prevent falls, help with swallowing safety, improve voice volume, and improve their ability to care for themselves.

Costs to the Subject

- Describe and justify any costs that the subject will incur as a result of participation; ordinarily, subjects should not be expected to pay for research without receiving direct benefit.

Subjects or their insurance provider will be responsible and billed for all costs related to your routine medical care, including co-payments and deductibles.

Data Analysis & Statistical Considerations

- Describe endpoints and power calculations. Provide a detailed description of how study data will be analyzed, including statistical methods used, and how ineligible subjects will be handled and which subjects will be included for analysis. Include planned sample size justification. Provide estimated time to target accrual and accrual rate. Describe interim analysis including plans to stop accrual during monitoring. Phase I studies, include dose escalation schema and criteria for dose escalation with definition of MTD and DLT.

The primary outcome is change in composite score on the self-efficacy scale. We will compare within subject change in score and differences in changes between control and experimental groups using repeated measures ANOVA.

Power calculations were performed using the published mean and SD for the self-efficacy scale. 73 participants per arm (control/experimental) for a total of 146 participants provides an 80% power to detect a 1 point change, which is felt to be a minimal clinically relevant change. We plan to recruit 100 participants per arm to account for any dropout. The maximum possible capacity of our benchmark clinic is 250 people per year for logistical/scheduling reasons so our sample size was chosen as a realistic number given our power calculation, total capacity, and expected interest of participants.

Secondary outcomes include change in total weekly minutes exercised, change in "engagement score" from the patient engagement survey (Likert scale 1-5 choices converted to 0, 25, 50, 75, and 100 to calculate composite engagement score as a mean of all Likert scale items), and change in Zarit (caregiver burden score). We will also compare total amount of skilled therapy visits, hospitalizations and ER visits, falls, and number of contraindicated medication combinations between the groups. All of these analyses will also be done using repeated measures ANOVA.

Subgroup analyses for the above outcomes will be performed using MOCA as a measure of baseline cognitive status and MDS-UPDRS as a measure of baseline disease severity both performed as linear regressions.

All enrolled subjects who complete the study visits will be included for analysis. Eligibility requirements are minimal (only need a diagnosis of Parkinson's disease) and those who do not have a diagnosis of Parkinson's disease will not be approached for this study, so we do not anticipate a significant number of ineligible

participants/screen failures. If for an unforeseen reason a participant is felt to not have a diagnosis of Parkinson's disease by a movement disorders specialist after enrollment, they will be removed from the study.

Estimated time to target accrual is 1 year with an accrual rate of 9 participants per arm per month.

RedCap and Duke Box will be used for data storage. A key will be used to link unique identifiers to participants responses. The key will be used to track completion of longitudinal data, as well as to query Duke Health medical records for health utilization (e.g. ED visits) as a secondary study outcome. The file connecting Study ID with Duke MRN will be encrypted and stored on the Duke Movement Disorders secure folder on the neurology private drive and will be password-protected. Only the study investigators will have access to this file.

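### The baseline survey behind the primary change score is completed after randomisation, and nothing in the protocol withholds the allocation until it is done

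*Combined protocol and SAP*

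**What the plan says.** The order of events is set out under Design & Procedures, Visit 1. On randomisation: "Participants will be randomized on a 1:1 basis to experimental vs control groups after consenting and prior to the start of this study visit". On the baseline measures: "Subjects will complete the pre-clinic quality of life, treatment adherence, and self-efficacy surveys at this visit". The motor examination falls on the same day, with the "motor disability score as part of normal clinic visit that day".

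Data Analysis & Statistical Considerations makes the Visit 1 score part of every participant's primary outcome: "The primary outcome is change in composite score on the self-efficacy scale". The analysis is a repeated measures ANOVA of within-subject change and of the difference in change between arms.

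Subject Recruitment and Compensation describes part of the pool: "All patients already scheduled for an upcoming benchmark clinic will be called or emailed to see if they would like to enroll". It adds that patients allocated to standard care "will have the opportunity to participate in the benchmark clinic within 1 year but not as part of this study".

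The protocol does not say when participants learn their arm. It has no statement on blinding, on delayed disclosure, or on completing the surveys before disclosure.

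**The concern.** The primary outcome comes from a survey that the participant fills in, and a clinic day cannot be masked against referrals once the arm is known. Some participants already hold a clinic booking when they are approached. For them, allocation to control means that they can attend only later and outside the study. A participant who knows this could rate their self-efficacy differently at Visit 1. The protocol does not say that this happens, but it does not prevent it.

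A change score is sensitive to this because the baseline is subtracted. A between-arm baseline shift that disappears by Visit 3 passes in full into the difference in change. One that partly persists passes in part, and one that fully persists cancels. If controls score low from disappointment and then recover, the trial is biased against the clinic and loses power. The reverse pattern would exaggerate the benefit.

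**Working it through.** **Order of events.** Consent, then randomisation, then the start of Visit 1, then the surveys. This is the protocol's explicit sequence, so the baseline is a post-allocation measurement whatever numbers follow.

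**The plan's own figure.** The protocol says "Power calculations were performed using the published mean and SD for the self-efficacy scale", and that "73 participants per arm (control/experimental) for a total of 146 participants provides an 80% power to detect a 1 point change". It states no SD, alpha or sidedness, so the figure cannot be reproduced independently. It can only be inverted. For a two-sample t-test with two-sided alpha 0.05 (assumed), 73 per arm, 1 point and 80% power:

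- standardised difference d = 0.467, so SD = 1 / 0.467 = 2.14
- standard error of the difference = 2.142 × √(2/73) = 0.355
- with the same SD and 100 per arm, standard error = 0.303 and power = 90.7%

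**Bias formula.** Net bias in the difference in change = baseline shift × (1 − fraction of the shift persisting to Visit 3). The shift sizes below are assumptions, because the documents give none.

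**Results.** Noncentral t, change SD 2.142. The power columns assume that the bias opposes a true 1-point effect.

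| Shift | Fraction persisting | Net bias | False positives, 73/arm | False positives, 100/arm | Power, 73/arm | Power, 100/arm |
|---|---|---|---|---|---|---|
| none | – | 0 | 5% | 5% | 80% | 91% |
| 0.25 | half | 0.125 | 6.4% | 7.0% | 68.8% | 82.0% |
| 0.25 | none | 0.25 | 10.8% | 13.0% | 55.6% | 69.3% |
| 0.5 | none | 0.5 | 28.8% | 37.6% | 28.8% | 37.6% |

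In the last row false positives and power coincide because the remaining effect, 1 − 0.5 = 0.5, equals the bias.

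**Direction.** Take the fully transient 0.25-point shift at 73 per arm, caused by low-scoring controls who then recover. Of the 10.8% false positives, 10.4 percentage points favour control and 0.4 favour the clinic. A simulation of 40,000 trials gave the same split.

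**Sensitivity to the SD.** The published SD may be a single-visit SD. If so, change SD = 2.142 × √(2(1 − r)), where r is the correlation between baseline and follow-up. At 73 per arm, with a fully transient shift:

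| r | Change SD | False positives, 0.25 shift | False positives, 0.5 shift |
|---|---|---|---|
| 0.3 | 2.53 | 9.1% | 22.0% |
| 0.5 | 2.14 | 10.8% | 28.8% |
| 0.7 | 1.66 | 14.8% | 44.0% |

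**Would baseline adjustment remove it?** Not fully. With equal variances at the two visits, the adjusted difference subtracts r × the baseline difference. With no shift left at follow-up, the bias is r × shift: 30%, 50% or 70% of it for r = 0.3, 0.5 or 0.7.

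**The case against.** The strongest objection is that moving the baseline ahead of allocation gives up the cancellation of a persisting shift. Suppose 75% of a 0.25-point reaction persists to Visit 3. Under the current order the net bias is 0.25 × 0.25 = 0.0625. With a clean baseline, the part still present at Visit 3 enters the change score: 0.25 × 0.75 = 0.1875. At 73 per arm, false positives go from about 5% to about 8%. Visit 3 is also answered with the arms known in practice. The arithmetic is right, but the conclusion does not follow. With a pre-allocation baseline, the difference in change is unbiased for the effect of being assigned to an arm. A reaction that lasts to Visit 3 is either part of that effect or a separate problem of an unmasked outcome. Contaminating the baseline to offset it is not a remedy.

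Several narrower points stand:

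- The shift sizes are hypothetical. The 0.5-point case is half of what the protocol calls a minimal clinically relevant change, and the milder case gives only 6% to 7% false positives. The illustration shows how the mechanism works and does not predict this trial's bias.
- The figures at 100 per arm assume no dropout, although the protocol recruits 100 to allow for it and analyses completers.
- The consent form was not available for this review. A disclosure rule stated only there would not have been seen.
- The conflict over the control arm's referral day (see the fix) is a separate matter and adds no weight to the bias argument.

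**Conclusion.** The concern holds and should be fixed. Two facts are firm: the protocol places randomisation before the survey that supplies the primary baseline, and it contains no safeguard against participants knowing their arm when they answer. Whether bias results, and in which direction, cannot be known from the documents.

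A plausible illustrative range at 73 per arm runs from 6% false positives and 69% power (half of a 0.25-point shift persisting) to 11% and 56% (none persisting). Larger shifts do more damage. These figures rest on an assumed shift, an assumed two-sided alpha of 0.05 and a back-solved SD of 2.14. More participants do not help, because a fixed bias produces more false positives at 100 per arm than at 73. The planned analysis offers no protection, and a contaminated baseline cannot be collected again.

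**What to change.** In Design & Procedures, Visit 1, place randomisation after the Visit 1 baseline surveys, and where feasible the motor score, have been completed and locked in REDCap. If randomisation must stay where it is, add: *The allocation is not disclosed to the participant or caregiver until the Visit 1 surveys are locked.*

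The cost is one sentence and an ordering rule in REDCap, which the protocol already names for data storage. There is no extra visit and no extra participant. The downside is that the allocation is known about 30 minutes later, partway through the clinic day. Putting the motor score first costs more, because it is done within the routine visit and randomisation would then fall during or after that visit. The surveys are therefore the minimum. The site should settle one order for the motor score and apply it to everyone.

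Separately, Design & Procedures describes the control group twice. The Visit 3 entry puts the control referrals on the day of Visit 2, and the paragraph that follows puts them on the day of Visit 1. The two must be reconciled. Completing the surveys first works with either.

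### If Visit 1 scores are unaffected by allocation, ANCOVA on the Visit 1 self-efficacy score is more precise than the planned change-score comparison

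*Combined protocol and SAP*

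**What the plan says.** In the combined protocol and SAP, *Data Analysis & Statistical Considerations* defines the endpoint: "The primary outcome is change in composite score on the self-efficacy scale". The analysis follows: "We will compare within subject change in score and differences in changes between control and experimental groups using repeated measures ANOVA". No baseline covariate is named. MOCA and MDS-UPDRS appear later in that section, but only in the subgroup regressions.

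*Design & Procedures* fixes the measurement times. Under Visit 1: "Subjects will complete the pre-clinic quality of life, treatment adherence, and self-efficacy surveys at this visit". Visit 3 is the only later survey point: "3-6 months Follow up study point surveys: approximately 30 minutes". The same section puts allocation first: "Participants will be randomized on a 1:1 basis to experimental vs control groups after consenting and prior to the start of this study visit". The Visit 1 score is therefore taken after randomisation, and no blinding is described.

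The analysis set is completers: "All enrolled subjects who complete the study visits will be included for analysis". On power, the plan says "Power calculations were performed using the published mean and SD for the self-efficacy scale" and "73 participants per arm (control/experimental) for a total of 146 participants provides an 80% power to detect a 1 point change", with 100 per arm to be recruited to cover dropout.

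**The concern.** With two arms and two time points, the arm-by-visit interaction in a repeated measures ANOVA is a two-sample t-test on change from Visit 1 to Visit 3. That test subtracts the whole Visit 1 score whatever its correlation with the Visit 3 score. When the correlation is well below 1, full subtraction adds noise. ANCOVA estimates the coefficient from the data instead.

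Precision is what is at stake. The Visit 1 score is already collected, and the planned analysis leaves part of its information unused. The same estimate could come with a narrower confidence interval from the same participants.

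**Working it through.** **Inputs.** From the documents: 1:1 randomisation, one score at Visit 1 and one at Visit 3, 73 per arm, 80% power, 1 point, 100 per arm recruited. Not given, so assumed: ρ (0.3, 0.5, 0.7), the SDs at the two visits, and two-sided alpha 0.05 (power only).

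**1. The plan's own figure.** The 73 per arm cannot be reproduced, because the SD, alpha, sidedness and any correlation are not stated. Solving backwards for a two-sample comparison at two-sided 0.05, 73 per arm and 80% power give a standardised difference of 0.467, so an SD of 1/0.467 = 2.14 points. That shows what 73 would be consistent with; it does not confirm it.

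**2. Precision, equal SDs.** Write σ for the SD at each visit. The variance of the arm difference is proportional to:

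- change score: 2σ²(1−ρ)
- ANCOVA: σ²(1−ρ²) = σ²(1−ρ)(1+ρ)
- ratio, ANCOVA to change: (1+ρ)/2

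| Assumed ρ | Ratio | Variance reduction | CI width ratio (square root) | Change-score completers equivalent to 100 under ANCOVA (100/ratio) |
|---|---|---|---|---|
| 0.3 | 0.65 | 35% | 0.806 | 154 |
| 0.5 | 0.75 | 25% | 0.866 | 133 |
| 0.7 | 0.85 | 15% | 0.922 | 118 |

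This needs no SD value, alpha or power assumption.

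**3. Unequal SDs.** Let k be the Visit 3 SD divided by the Visit 1 SD. In units of the Visit 1 variance, change has 1 + k² − 2ρk and ANCOVA has k²(1−ρ²). The difference is (1−ρk)², which is never negative. So ANCOVA is never less precise, apart from one degree of freedom. At ρ of 0.3, 0.5 and 0.7:

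- k = 1.2: ratios 0.762, 0.871, 0.966 (reductions of 24%, 13%, 3%)
- k = 0.8: ratios 0.502, 0.571, 0.628 (reductions of 50%, 43%, 37%)

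**4. Power, as illustration only.** Take the SD of 2.14 as that of a single score, equal at both visits, with a 1-point between-arm difference. Noncentral t, planned test against ANCOVA, at ρ of 0.3, 0.5 and 0.7:

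- 73 completers per arm: 66% v 84%, 80% v 90%, 95% v 97.5%
- 100 completers per arm: 79% v 93%, 91% v 97%, 98.9% v 99.6%

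If the SD behind 73 is already that of change, the planned test has 80% at 73 per arm, and ANCOVA has 94%, 90% and 86%. If 73 was sized from a single-score SD with an assumed ρ of 0.7, the planned test has 45%, 58% and 80%; with an assumed 0.3, it has 80%, 91% and 99%. The spread shows how little the power figures can be pinned down. The variance ratios carry the point.

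**5. Visit 1 measured after allocation.** Let D₁ and D₃ be the arm differences at Visits 1 and 3. The ANCOVA estimate is D₃ − βD₁ = (1−β)D₃ + β(D₃−D₁). For a slope β between 0 and 1 it lies between the unadjusted Visit 3 comparison and the change-score comparison. With equal SDs β is about ρ. Suppose knowing the allocation shifts the experimental arm's self-report by b:

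| Shift | Bias, change score | Bias, ANCOVA | Bias, unadjusted Visit 3 |
|---|---|---|---|
| Visit 1 only | −b | −ρb | 0 |
| Both visits | 0 | (1−ρ)b | b |

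With an assumed b of 0.5 point, ANCOVA is biased by −0.15, −0.25 and −0.35 in the first case and by 0.35, 0.25 and 0.15 in the second. Simulations with no true effect, SD 2.14 and 73 per arm agree. For a shift at both visits, rejection at nominal 5% was 4.8%, 5.2% and 5.1% for change scores and 18.0%, 12.8% and 9.1% for ANCOVA. For a shift at Visit 1 only, computed rejection was 22.0%, 28.8% and 44.0% for change scores and 7.2%, 12.7% and 27.6% for ANCOVA.

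**The case against.** The strongest reply concerns the baseline. Participants are allocated before they fill in the Visit 1 survey, so ANCOVA would condition on a score that allocation may have moved. If knowing the allocation shifts self-report equally at both visits, change scores cancel the shift and ANCOVA does not. Likewise, if analysing completers only leaves a stable difference between the arms, change removes it and ANCOVA does not fully. This stands. A reader might infer that ANCOVA costs nothing here, or that it always reduces bias from the late survey. The documents support neither, because they do not show whether any shift exists or how long it would last. Nor does this defend the planned test, which has the larger bias if the shift is at Visit 1 only. *Design & Procedures* also places the control arm's referrals on the day of Visit 2 in one paragraph and of Visit 1 in the next. These must be reconciled, since they bear on whether the Visit 1 score precedes arm-specific care.

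A second reply is that the gain may be slight. This also stands: at ρ = 0.8 the first illustration moves only from 99.3% to 99.7% at 73 per arm, and at ρ = 0.7 with k = 1.2 the variance falls by 3%.

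Third, the planned analysis does use the Visit 1 score, with its coefficient fixed at 1. To say that it ignores baseline would be wrong.

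Fourth, the objective is framed against standard care and the analysis sentence names the difference in changes between arms, so the intended comparison can be inferred. Not labelling it primary is missing detail, as are the unstated power inputs.

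**Conclusion.** The point holds as a conditional efficiency improvement. Given a Visit 1 score unaffected by allocation and no bias from analysing completers only, ANCOVA estimates the same between-arm difference. With equal SDs its variance is 35%, 25% and 15% lower at assumed ρ of 0.3, 0.5 and 0.7. The algebra is certain. The size in this trial is not, because the documents give neither ρ nor the SDs.

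Three stronger readings are tempting and not supported:

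- *The planned test is invalid, or the 80% power is wrong.* Under the same conditions the change-score test is valid. The power cannot be checked from what is stated, which does not make it wrong.
- *The gain is largest when many drop out.* The variance ratio does not depend on the number of completers, apart from one degree of freedom. In the power illustration at ρ = 0.3 the gain is 13.8, 18.5 and 13.8 percentage points at 30, 60 and 100 per arm, so it does not rise steadily with dropout.
- *Switching to ANCOVA deals with the survey being taken after randomisation.* It does not; the direction of any remaining bias is unknown.

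**What to change.** Replace the primary analysis sentence with wording such as: *The primary analysis is an ANCOVA of the Visit 3 self-efficacy composite on arm, with the Visit 1 composite as covariate. The adjusted between-arm difference with its 95% confidence interval is the primary test; within-arm changes are descriptive.* ANCOVA of the change score on arm and Visit 1 score gives the identical arm estimate, so the declared outcome can stay.

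In *Design & Procedures*, have the Visit 1 survey completed after consent but before allocation is made or disclosed, so that the covariate is a true baseline. If the order cannot change, prespecify the change-score and unadjusted Visit 3 comparisons as sensitivity analyses. For a slope between 0 and 1 they lie on either side of the ANCOVA estimate, and each is free of bias under one of the two shift patterns above.

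The cost is one rewritten analysis sentence, one change in the order of Visit 1 and one degree of freedom. No extra data, visits or participants are needed. If the survey stays after allocation, residual bias of unknown direction remains possible. The completers-only analysis set is a separate matter that this change does not settle.
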